Lamotrigine Dosing Adjustments. At the time of study enrollment each participant will have a RC defined based on either 1) a pre-pregnancy serum level (for the current lamotrigine dosage) or 2) a serum level drawn at the time of enrollment. While we will preferentially use a pre-pregnancy RC since pregnancy hormone levels can affect lamotrigine levels, many psychiatrists do not routinely check lamotrigine levels and from a practical perspective we will obtain a lamotrigine at study entry to promote study participation and recruitment. Participants will be clinically well at the time of enrollment so that the serum level will be correlated with clinical stability. Lamotrigine levels will then be drawn monthly and the dose adjusted to maintain the RC. Specifically, if the monthly serum level is more than 0.5µg/mL lower than the RC, the dose will be adjusted by 20-25% and checked again at the next monthly visit. Higher levels than the RC are unlikely, since levels generally decrease across the course of pregnancy, but the dose will not be adjusted down unless there is a clinical indication (i.e. toxicity). Postpartum, all participants will be instructed to taper to the lamotrigine dose that was being taken at the time of the RC over the course of two weeks. While this does not follow the exact neurology, protocol described above (Background), we believe this approach makes sense since it will be more consistent and avoid the potential problem of toxicity. It also follows the recommendations of Clark et al²³.

Data Collection

a) **Maternal Psychiatric Outcomes:** We will monitor maternal psychiatric outcomes based on the EPDS, YMRS and clinical interview. The primary endpoint is the proportion of women who experience psychiatric relapse from the time of enrollment to 6 weeks postpartum. **Relapse** will be defined as one of the following: meeting SCID criteria for a Major Depressive Episode, meeting SCID criteria for a hypomanic or manic episode, development of high risk suicidal plan or attempt, or psychiatric hospitalization.

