b) **Maternal Adverse Event Outcomes:** Adverse events will be monitored by using a semi-structured interview, (the UKU side effects rating scale) at every visit as well as the self-rated Frequency, Intensity and Burden of Side Effects Rating scale (FIBSER). Adverse events will be considered as related to the TDM protocol if they were not present at baseline or worsened in severity and were noted after a change in dosing. A preliminary analysis will be conducted comparing adverse events in participants who underwent dose increases during pregnancy to those that did not (assuming there are participants who did not undergo dosage increase).

c) **Maternal Obstetrical Outcomes:** Maternal obstetrical outcomes will be extracted from the delivery admission chart which will be reviewed by the study obstetrician, [name]. The Perinatal Events Scale (PES) will be used to collect a majority of these outcomes including Past Obstetrics History, Medical Risk Factors, Obstetric Risk Factors, Progress in Labor, Method of Delivery and Complications. A preliminary analysis will be conducted comparing obstetrical outcomes in participants who underwent dose increases in pregnancy to those that did not (assuming there are participants who did not undergo dosage increase).

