- e. **Justification for inclusion of a placebo or non-treatment group.** There will be no placebo or non-treatment group.

- f. **Definition of treatment failure or participant removal criteria.** Participants will be removed from the study if they meet criteria for Relapse as described above. Participants will also be removed if they are lost to follow-up or are noncompliant with the study protocol.
- g. **Description of what happens to participants receiving therapy when study ends or if a participant's participation in the study ends prematurely.** Participants will return for clinical care to their outpatient provider at the end of the study or if their participation ends prematurely.

5. Inclusion/Exclusion Criteria

Inclusion Criteria. Pregnant women with a history of Bipolar Disorder (Bipolar Disorder I, Bipolar Disorder II or Bipolar Disorder not otherwise specified) who are taking lamotrigine and who intend to continue lamotrigine through pregnancy will be enrolled. All participants must be in the first 20 weeks of pregnancy at the time of enrollment. All participants must also be on stable doses of lamotrigine (for the past 4 weeks), have an EPDS <13, a YMRS <12 and be judged by the study clinician to be clinically stable. Participants may be taking other psychiatric and nonpsychiatric medications.

Exclusion Criteria. Participants who have active suicidal ideation or who are clinically unstable will be excluded. Participants who are dependent on alcohol, marijuana or other substances in the 90 days prior to study entry will be excluded.

6. Drugs/ Substances/ Devices

- a. **The rationale for choosing the drug and dose or for choosing the device to be used.** Lamotrigine is an evidence-based treatment for Bipolar Disorder in pregnancy. The rationale for our TDM/dosing regimen is based on recommendations in the epilepsy literature. There is currently no established protocol for the dosing of these drugs in pregnant patients with Bipolar Disorder.
- b. **Justification and safety information if FDA approved drugs will be administered for non-FDA approved indications or if doses or routes of administration or participant populations are changed.** There are no drugs with FDA approval for the management of mood disorders in pregnancy. Therefore, we must use FDA approved drugs for non-FDA approved indications, a common clinical practice.

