- If the participant is not at risk of harming herself or others but is psychiatrically ill, the study psychiatrist will provide clinical care as necessary until the participant can be seen by her treating outpatient clinical psychiatrist. The participant will remain in the study and undergo all study visits and procedures as long as consent continues.

Obstetrical Urgency/Emergency: Should one of the participants develop an urgent obstetrical problem, the participant will either be taken to the local Obstetrics and Gynecology Clinic or Emergency Room, whichever seems more appropriate. Both the Clinic and the Emergency Room are on the same campus as the study site. The subject's private obstetrician will also be contacted.

Lamotrigine toxicity: Every participant will be monitored closely for side effects/signs of toxicity during the trial. Because the RC will be established prior to pregnancy or early in pregnancy we anticipate that the likelihood of significant side effects or toxicity in the participants is very low. If a participant does develop side effects or signs of toxicity the dose of lamotrigine will be lowered by the study psychiatrist. At every visit the participant will fill out a Frequency, Intensity and Burden of Side Effect Scale (FIBSER) to monitor for significant side effects from the protocol. Obstetrical outcomes will be assessed by [name] from the Gynecology and Obstetrics Department.

Neonatal toxicity: It is possible that increased dosing of lamotrigine during pregnancy will lead to increased side effects or toxicity in the newborn. We do not anticipate this outcome since the protocol is used in the management of seizure disorders and there have not been reports of adverse effects in infants whose mothers participate in these protocols. We will monitor for this potential risk by collecting neonatal outcomes via a review of the medical record by a pediatrician ([name]) and by undergoing a neurobehavioral exam using the Neonatal Intensive Care Unit (NICU) Network Behavioral Scale (NNNS) at 2, 4, and 6 weeks postpartum. Our research assistant will undergo specialized training at Brown University in order to conduct the exam appropriately.

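### Section 4.f removes every woman who relapses while Section 8.b keeps some of the same women in all visits; if 4.f is followed, later side-effect ratings and infant neurobehavioral exams are lost

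*Protocol*

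**What the plan says.** Section 4.f of the protocol, on treatment failure and removal, says: "Participants will be removed from the study if they meet criteria for Relapse as described above". It makes no exception. Relapse is defined in Section 4.a (Maternal Psychiatric Outcomes) and again in Section 7. Any one of several events suffices, including "meeting SCID criteria for a Major Depressive Episode, meeting SCID criteria for a hypomanic or manic episode". The other qualifying events are a high-risk suicidal plan or attempt and psychiatric hospitalization.

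Section 4.g describes what follows an early end of participation: "Participants will return for clinical care to their outpatient provider at the end of the study or if their participation ends prematurely". It mentions no further study assessment.

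Section 8.b, under Psychiatric Urgency/Emergency, sets a different rule. It opens with "If the participant is not at risk of harming herself or others but is psychiatrically ill", provides for interim care by the study psychiatrist, and then says: "The participant will remain in the study and undergo all study visits and procedures as long as consent continues".

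Three data-collection provisions depend on which rule applies:

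- **Maternal adverse events** (Section 4.a): "Adverse events will be monitored by using a semi-structured interview, (the UKU side effects rating scale) at every visit". The self-rated FIBSER is also completed at every visit (8.b, Lamotrigine toxicity).
- **Infant neurobehavior** (Section 4.a, Newborn Outcomes): an NNNS exam for all infants at 2, 4 and 6 weeks postpartum.
- **Newborn toxicity** (8.b, Neonatal toxicity): the protocol accepts that higher dosing might harm the newborn and says "We will monitor for this potential risk by collecting neonatal outcomes via a review of the medical record by a pediatrician", together with the NNNS exams.

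**The concern.** A woman with a SCID depressive, hypomanic or manic episode who poses no risk of harm falls under both rules. Section 4.f takes her out of the study, and 8.b keeps her in every visit and procedure. Nothing in 8.b confines it to illness below the Relapse threshold, and nothing says which rule prevails. Staff could handle similar women differently.

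The larger stake is what happens if 4.f is followed. Maternal adverse-event follow-up (Aim 2) then ends at relapse. Infants whose mothers relapse before the exams lose the NNNS part of the toxicity monitoring. Some of those infants may have been exposed to increased doses; the protocol does not say how many. The data are then missing because of the study's own outcome, and the planned comparisons of women with and without dose increases would rest on what remains.

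**Working it through.** **1. Do the two rules cover the same woman?**

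| Situation | Section 4.f | Section 8.b, last psychiatric bullet |
|---|---|---|
| SCID episode, no risk of harm | Removed | Stays in all visits |
| High-risk suicidal plan or attempt | Removed | Not covered |
| Psychiatrically ill, Relapse not met, no risk of harm | Not removed for relapse | Stays in all visits |

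The first row is a direct conflict. It is unlikely to be rare, because the Abstract says that most relapses on continued medication are depressive.

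**2. What is lost if 4.f is followed?** UKU and FIBSER are done at visits, so ratings after removal are lost. A relapse in pregnancy, or after delivery but before week 2, loses all three NNNS exams. A later relapse loses those still to come. Delivery-chart review needs no visit. The protocol neither provides for it after removal nor says that it stops.

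**3. How many women?** Inputs: n = 20 (Section 4.a, Sample Size; the plan's own figures reconcile, 20 − 4 drop-outs = 16) and p = 0.30 (Section 7, the expected rate without the protocol's dosing). The rates p = 0.20 and 0.10 are assumptions for the case where TDM works. Relapses are taken as Binomial(20, p):

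- expected removals = 20p
- P(at least one relapse) = 1 − (1 − p)^20

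| p | Expected removals | Central 95% range | P(at least one) |
|---|---|---|---|
| 0.30 | 20 × 0.30 = 6 | 2–10 | 1 − 0.70^20 = 99.9% |
| 0.20 | 20 × 0.20 = 4 | 1–8 | 1 − 0.80^20 = 98.8% |
| 0.10 | 20 × 0.10 = 2 | 0–5 | 1 − 0.90^20 = 87.8% |

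**4. How many before delivery?** The protocol does not give the share of relapses that occur before delivery, so the full range of 0 to 100% is used. Removals before delivery = 20p × share, which gives 0–6, 0–4 and 0–2. The Abstract speaks of high relapse during pregnancy despite continued medication, so some removals before delivery are foreseeable.

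**5. How many NNNS exams?** Planned exams: 20 infants × 3 = 60, assuming one infant per woman. The minimum loss is 0, if every relapse is found at the week-6 visit. The maximum is 3 × 20p, if every relapse comes before week 2:

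- p = 0.30: 0–18 of 60
- p = 0.20: 0–12 of 60
- p = 0.10: 0–6 of 60

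All figures in steps 3 to 5 assume that 4.f, not 8.b, is applied to every relapse.

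**The case against.** The strongest defense is that the two rules can be reconciled. Section 4.f uses a defined term under a heading about removal. The 8.b sentence closes a list of procedures for limiting suicide risk and uses undefined clinical language. It could mean symptoms short of a SCID episode, with 4.f taking over once Relapse is met. But the text states no such limit, and a bullet about interim psychiatric care fits an acute episode at least as well. Even on that reading, 4.f would still end safety follow-up for every woman who relapses.

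Several narrower points stand:

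- The contradiction concerns only women with an episode and no risk of harm. The counts above cover all relapses, as 4.f does, so they are an upper bound for the conflict itself.
- The NNNS ranges all start at zero because timing is unknown. On the 16 women the protocol hopes to retain, the base is 16 × 3 = 48 exams and the maximum losses are 14.4, 9.6 and 4.8.
- Chart review may continue, so no loss is shown for Aim 3 or for the chart part of Aim 4.
- The rule that all infants are examined might be read to include those of removed mothers, although 4.g provides no visits for them.
- Aims 2 to 4 are preliminary and descriptive.

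These points limit the size of the problem. They do not remove the conflict or the loss of visit-based safety data under 4.f.

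**Conclusion.** The concern holds, and the text should be corrected. The two sections contradict each other for a woman with a SCID episode and no risk of harm. Even at an assumed 10% relapse rate, the chance that 4.f comes into play at least once among 20 women is about 88%.

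The expected loss runs from 2 to 6 women and from none to 18 of 60 NNNS exams. This rests on 20 women followed, independent relapses at 10% to 30%, one infant each, and 4.f being applied. Confidence is high in the contradiction and in the fact that visit-based follow-up would stop. The number of exams lost cannot be narrowed from the document, and neither can the direction of any distortion in Aims 2 to 4. The primary endpoint is not affected, because a woman removed at relapse already has a known outcome.

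**What to change.** Replace the relapse sentence in Section 4.f with:

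*Relapse is the primary endpoint event and counts as treatment failure. TDM dosing may stop, but the woman and her infant remain in adverse-event, delivery-chart and NNNS follow-up to 6 weeks postpartum as long as consent continues.*

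Align 8.b so that it covers all women who relapse, including those at risk of harm once they have been clinically managed. Including the at-risk women goes beyond what is needed to resolve the contradiction, but their infants need the same monitoring.

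Report adverse events after relapse separately. Section 4.a relates an event to TDM if it was new or worse and if such events "were noted after a change in dosing", which is harder to judge once treatment has changed.

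The cost is a wording amendment. The visits are already planned for up to 20 women, and 8.b already foresees them for some. The downsides are extra effort to retain women who are unwell and weaker attribution of later events. Whether the consent text would also need to change cannot be checked, because the consent pages are not in the public copy.

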Our primary hypothesis is that prophylactic TDM for lamotrigine will result in a lower than expected rate of psychiatric relapse. The study will be an unblinded pilot study testing a TDM protocol for lamotrigine and will examine psychiatric, adverse event, obstetrical and infant outcomes. Because this is a pilot study we have chosen not to recruit a comparison group of women and instead focus on collecting outcomes for a larger sample of women who will undergo TDM for lamotrigine. Based on the literature we would expect the relapse rate in women who are maintained on their pre-pregnancy lamotrigine dosage to be at least 30%^{1,2}. Although our study design will not demonstrate superiority, it will provide preliminary evidence of efficacy and safety data for both the participant and her infant and will be the largest study examining a specific approach to managing lamotrigine during pregnancy in patients with Bipolar Disorder. We hope these data will then serve as a basis for a multisite randomized trial of prophylactic TDM for lamotrigine compared to treatment as usual in the future.

Pregnant women with Bipolar Disorder who are taking lamotrigine will be evaluated monthly during pregnancy including a clinical evaluation and a blood draw for lamotrigine levels at each visit. Based on the TDM protocol described below their lamotrigine dosing will be adjusted as needed based on their blood levels compared to the RC that was obtained prior to pregnancy or early in pregnancy while clinically stable. After delivery women and their infants will be assessed at 1, 2, 4, and 6 weeks postpartum.

Sample Size. We will recruit and follow up to 20 women with Bipolar Disorder who have chosen to take lamotrigine during pregnancy with a goal of maintaining a sample size of 16 allowing 4 drop-outs.

Recruitment. Participants will primarily be recruited through the Johns Hopkins Women's Mood Disorders Center (WMDC) and through referrals from the Obstetrics department. We will advertise on the WMDC Facebook site, the WMDC research site, EPIC and in local publications.

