d) **Newborn Outcomes:** Newborn outcomes will be extracted from the delivery admission chart which will be reviewed by the study pediatrician, [name]. We will use the infant outcomes portion of the Peripartum Events Scale (which includes Apgar scores and Infant Complications) and, in addition, collect infant weight, measurements, gestational age and need for medical interventions or NICU admission. A preliminary analysis will be conducted comparing infant outcomes for participants who underwent dose increases during pregnancy to those that did not (assuming there are participants who did not undergo dosage increase). All infants will also undergo a neurobehavioral assessment at weeks 2, 4 and 6 postpartum using the Neonatal Intensive Care Unit (NICU) Network Behavioral Scale (NNS). Our research assistant will receive training at the Brown Center for the Study of Children at Risk which has a standardized training on the use of NNS. The NNS will be used to identify any infant neurobehavioral effects of the TDM protocol. A preliminary analysis will be conducted comparing infant neurobehavioral outcomes for participants who underwent dose increases during pregnancy to those that did not (assuming there are participants who did not undergo dosage increase).

- b. **Study duration and number of study visits required of research participants.** Each subject will be seen approximately 12 times across the course of the study. We will attempt to recruit subjects who are less than 20 weeks pregnant and will plan for monthly study visits during pregnancy. Women and their infants will also be assessed after delivery at 1, 2, 4, and 6 weeks postpartum. We expect that most study visits will take place in the Women's Mood Disorders Center, however home visits by research assistants will be used if a participant cannot come to the Center (for example if a participant is on bedrest) to maintain participation and continuity.
- c. **Blinding, including justification for blinding or not blinding the trial, if applicable.** Not applicable. Subjects will be receiving the drug that is part of their usual care and we will be collecting pilot data.
- d. **Justification of why participants will not receive routine care or will have current therapy stopped.** Participants will undergo more clinical care than is currently routine in that they will be monitored on a monthly basis and their lamotrigine dosing adjusted as part of a TDM protocol.

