- c. **Justification and safety information if non-FDA approved drugs without an IND will be administered.** Not applicable.

7. Study Statistics.

We will perform descriptive statistics that include percent tabulations for categorical variables, means with standard deviations for continuous variables, and medians with ranges where more appropriate. The primary endpoint is the proportion of women who experience psychiatric relapse from the time of enrollment to 6 weeks postpartum. Relapse will be defined as one of the following: meeting SCID criteria for a Major Depressive Episode, meeting SCID criteria for a hypomanic or manic episode, development of high risk suicidal plan or attempt, or psychiatric hospitalization. We do not have a comparison group but would normally expect a relapse rate of approximately 30% based on the literature We will also collect and describe adverse events, obstetrical and infant outcomes.

8. Risks.

a) **Medical Risks.** The risks and discomforts are expected to be minimal and rare. During interviews, the participants may experience some discomfort or anxiety because of the personal nature of the questions. There may be some risk that the research participant may find the diagnostic interview uncomfortable or feel it is an invasion of privacy. Venipuncture may be associated with the momentary discomfort of the needle stick, fainting, bruising and rarely infection. There is also a risk for loss of confidentiality. Other risks include maternal side effects or toxicity from lamotrigine, infant side effects or toxicity from lamotrigine, and maternal psychiatric relapse.

b) **Steps Taken to Minimize Risks:**

Interviews, Questionnaires: A trained research assistant will be available at all times while the participant is filling out questionnaires. The Principal Investigator will also be available by telephone, and WMDC clinicians (including a psychiatrist) will be onsite during the administration as well. Should the participant become distressed, the study staff member can provide reassurance and evaluate her psychiatric state. Participants will be informed during screening and consenting procedures that they do not have to answer or complete tasks that cause them distress. Each participant will be directed to inform the study team member if she wishes to skip a certain part. If the study staff member determines that the participant is experiencing a psychiatric emergency, the steps listed below under that heading will be taken.

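### Section 4.f removes every woman who relapses, while section 8.b keeps an ill woman who is not at risk of harm in all visits; applying 4.f cuts off safety follow-up

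*Protocol*

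**What the plan says.** Section 4.f, which covers treatment failure and participant removal together, reads: "Participants will be removed from the study if they meet criteria for Relapse as described above". Section 4.g then returns a woman whose participation ends early to her outpatient provider. No section provides for study follow-up after removal.

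Relapse is defined identically in section 4.a (Data Collection, a) and section 7. Any one of four events is enough. The first two are "meeting SCID criteria for a Major Depressive Episode, meeting SCID criteria for a hypomanic or manic episode", and neither carries a risk-of-harm condition. The others are a high-risk suicidal plan or attempt and psychiatric hospitalization.

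Section 8.b (Psychiatric Urgency/Emergency) sends a woman judged at risk to emergency care. Its last bullet covers the rest: "If the participant is not at risk of harming herself or others but is psychiatrically ill", the study psychiatrist provides interim care, and "The participant will remain in the study and undergo all study visits and procedures as long as consent continues".

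The data and care that depend on staying in the study are:

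- The UKU interview (section 4.a, Data Collection, b) and FIBSER (section 8.b, Lamotrigine toxicity), both at every visit.
- The infant NNNS examination (section 4.a, Data Collection, d): "All infants will also undergo a neurobehavioral assessment at weeks 2, 4 and 6 postpartum".
- The return to the dose taken when the reference concentration (RC) was set (section 4.a, Lamotrigine Dosing Adjustments): "Postpartum, all participants will be instructed to taper".

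**The concern.** Relapse is the event this study is built around, and the two sections give staff opposite instructions when it occurs without risk of harm. One ends participation; the other continues every visit and procedure.

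The choice matters for safety. Under the dosing algorithm the study may have raised a woman's dose in one or more 20-25% steps. The taper after delivery is meant to avoid toxicity, and the Background section reports a rise of up to 600% in the level-dose relationship after childbirth. Section 8.b also names the NNNS examination as part of its monitoring for neonatal effects of increased dosing. If 4.f is followed, women who relapse before delivery leave before any of this takes place. Aims 2 and 4 then lack part of their data for exactly those women.

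**Working it through.** **1. Does one woman fall under both rules?**

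| Participant | 4.f | 8.b, last bullet |
|---|---|---|
| SCID episode, no risk of harm | removed | retained for all visits |
| SCID episode or other relapse, at risk of harm | removed | does not apply |
| Ill but below SCID criteria, no risk of harm | does not apply | retained |

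The rules collide only in the first row. Section 8.b sorts women by risk of harm, not by SCID status, so a SCID episode without risk is inside its wording. No precedence is stated.

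**2. What does one woman lose if 4.f is applied before delivery?**

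Inputs: about 12 visits in total (section 4.b), of which 4 are postpartum, at weeks 1, 2, 4 and 6.

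- Pregnancy visits: 12 - 4 = about 8. A woman enrolled near 20 weeks has fewer, but the 4 postpartum visits do not change.
- Side-effect assessments lost if removed at the last pregnancy visit: 12 - 8 = 4. If removed at pregnancy visit 4 (illustration): 12 - 4 = 8.
- NNNS examinations lost: weeks 2, 4 and 6, so 3 of 3 in either case.
- Taper: the instruction is given postpartum, so she leaves before it. A woman removed after completing the two-week taper does not lose it.

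Not necessarily lost: the primary endpoint, because relapse has been counted by the time she is removed; and the obstetric and newborn outcomes taken from the delivery chart, which are not expressly limited to women still in the study. Aim 4 therefore loses its NNNS part, not all of its data.

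**3. How many women would 4.f remove?**

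The plan's own arithmetic (section 4.a, Sample Size) is up to 20 recruited less 4 drop-outs: 20 - 4 = 16, which reproduces. Expected removals are n x relapse rate:

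| Relapse rate | Source | Of 20 | Of 16 |
|---|---|---|---|
| 10% | assumption | 2.0 | 1.6 |
| 20% | assumption | 4.0 | 3.2 |
| 30% | sections 1 and 7 | 6.0 | 4.8 |
| 37% | section 1, upper figure | 7.4 | 5.9 |

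The two assumed rates lie within the protocol's hypothesis of below 30%. Even at 10%, the chance that 4.f is triggered at least once among 20 women is 1 - 0.9^20 = 0.88.

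These counts cover all relapses. The documents give neither the share without risk of harm, where the two rules conflict, nor the share occurring before delivery, where the loss in step 2 is complete.

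**The case against.** The strongest reply is that the rules can be reconciled. Section 4.f is the dedicated removal section and uses a defined term. The 8.b sentence is one bullet in an emergency procedure and uses an undefined description of illness. If the specific rule governs, 8.b covers only illness short of Relapse. That reading is possible, but it is not in the text, which draws its line at risk of harm. It also leaves the practical problem in place: every woman who relapses would then be removed, with no follow-up afterwards.

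A second reply is that stopping at the endpoint is a legitimate choice in a descriptive pilot. For Aim 1 it is. Aims 2 and 4, however, concern the safety of doses the study itself may have raised, and that exposure does not end with relapse.

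Third, 4.g returns the woman to her own provider, and section 8.b already keeps provider contacts and signed releases on file. This stands as a mitigation. But nothing requires the RC, the dose at the RC or the taper instruction to be passed on. It is also fair to say that the protocol describes an instruction to taper and specifies no postpartum level monitoring, so what is lost should not be called more than that.

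Fourth, a reader might set the expected removals against the sample-size statement, "with a goal of maintaining a sample size of 16 allowing 4 drop-outs", and infer that relapse alone would probably take the study below 16. The document does not support this. It does not say that relapse counts as a drop-out, nor that the 16 must be followed to 6 weeks postpartum, and a woman who relapses is fully evaluable for the primary endpoint.

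**Conclusion.** The contradiction stands for women who meet Relapse through a SCID episode without risk of harm. It should be settled in the protocol, because staff have to act on it at a visit. If 4.f prevails, each woman removed before delivery loses 3 of 3 NNNS examinations, at least 4 of about 12 side-effect assessments and the taper instruction. If 8.b prevails, a woman in the overlap keeps all of these.

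Across 20 women, 4.f would remove an expected 2.0 to 7.4 at relapse rates of 10% to 37%. This assumes that 20 are enrolled and none leaves first for another reason. It is an upper bound on the number in conflict, since the share without risk of harm is unknown.

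Three stronger conclusions are not supported: that the primary endpoint is compromised, that Aim 4 as a whole is lost, and that the target of 16 would be missed. No direction of bias is shown either. This is a correction the study should make, not a flaw that invalidates it.

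**What to change.** Amend 4.f to say that relapse is the endpoint (treatment failure) but is not a reason for removal, and that consenting women continue adverse-event, delivery-chart and infant follow-up to 6 weeks postpartum. This brings 4.f into line with what 8.b already promises to some of these women.

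Add to 4.g: where a woman still leaves before delivery on a study-raised dose, send the RC, the dose at the RC, the current dose and the taper instruction to the outpatient provider on file, and to the woman herself where she can be reached. A woman lost to follow-up may not be reachable, so the provider is the route that matters.

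The cost is a short amendment, a brief handover note, and visit payments and lamotrigine level tests already planned for every participant. No extra patients are needed. For a woman retained after pregnancy visit 4, section 10 implies:

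- Under its $450 total: already paid 4 x $25 = $100, so at most $450 - $100 = $350 more.
- At its listed rates, ignoring that total: 4 x $25 + 4 x $75 + $100 bonus = $500 more.

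The level tests come on top of either figure; the protocol gives no price for them.
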